6.8 Assessment of Study Intervention Compliance

Berzosertib will be administered under the direct supervision of the Investigator or designee. For all doses of the study intervention, the number of units administered and missed doses will be recorded in the eCRF. All modifications in study intervention dose or interval between dosing, as well as the reason for modification, will be recorded in the eCRF.

6.9 Blinding

Not applicable.

6.10 Emergency Unblinding

Not applicable.

6.11 Treatment of Overdose

An overdose is defined as any dose greater than the highest daily dose included in a clinical study protocol or planned for an individual participant enrolled in the study. Even if it does not meet other criteria for a serious adverse event (SAE), any overdose must be recorded in the study medication section of the eCRF and reported to Drug Safety in an expedited manner using the SAE Report Form, and following the procedure in Section 7.4.

For dose modification and toxicity, refer to the Dose Modification for Toxicity section from the VX13-970-002 protocol.

Document No. CC	C O N F I D E N T I A L I N F O R M A T I O N	22/54
	Blobal Version ID: CC	

6.12 Medical Care of Participants after End of Study

After a participant has completed the study or has been withdrawn, further treatment will be administered, if required, in accordance with the study site's Standard of Care and generally accepted medical practice depending on the participant's individual medical needs.

The Sponsor will not provide any additional care to participants after they leave the study because such care should not differ from what is normally expected for participants with advanced tumors.

7 Study Procedures and Assessments

7.1 Schedule of Assessments

Prior to performing any study assessments that are not part of routine medical care for the participant, the Investigator will obtain written informed consent as described in Section 9.2.

A detailed Schedule of Assessments is provided in Table 1.

7.1.1 Enrollment

Participants still on active study intervention at the termination/transition of the VX13-970-002 will be enrolled in this Safety Follow Up study.

7.1.2 Treatment

The participant will continue treatment at the same dose and according to the same schedule as in the VX13-970-002 study.

7.1.3 Safety Follow Up

Safety Follow Up will include a Safety Follow Up visit to be scheduled 28 (+7) days after the last administration of berzosertib. Participants will be treated according to institutional standards of care, including monitoring of disease progression.

7.2 Demographic and Other Baseline Characteristics

At enrollment, the following demographic data will be documented in the eCRF: date of birth, sex (gender), race, and participant identifier from the parent study.

7.3 Efficacy Assessments

Not applicable.

7.4 Assessment of Safety

The safety profile of the study intervention will be assessed through the recording, reporting and analysis of the nature, occurrence, and severity of treatment-emergent adverse events (TEAEs).

Document No. CC	C O N F I D E N T I A L I N F O R M A T I O N	23/54	
Object No. CC	Global Version ID: CCI		

Physical examination, weight, vital signs, serum chemistry, hematology and urinalysis will be measured as per Standard of Care and institutional guidelines and as clinically indicated; only clinically significant values should be reported as AEs.

A clinically significant value is a result that a clinician would consider to be medically meaningful. Clinically significant values may be more severe than values expected for the participant's condition, age, and gender.

Comprehensive assessment of any apparent toxicity experienced by each participant will be performed from the time of giving informed consent and throughout the study. The Investigator will report any AEs, whether observed by the Investigator or reported by the participant (see Section 7.4.1.2). The reporting period for AEs is described in Section 7.4.1.3.

7.4.1 Adverse Events

7.4.1.1 Adverse Event Definitions

Adverse Event

An AE is any untoward medical occurrence in a participant or clinical investigation participant administered a pharmaceutical product, regardless of causal relationship with this treatment. An AE can therefore be any unfavorable and unintended sign (including an abnormal laboratory finding), symptom, or disease temporally associated with the use of a medicinal product, whether or not considered related to the medicinal product.

For surgical or diagnostic procedures, the condition/illness leading to such a procedure is considered as the AE rather than the procedure itself.

The Investigator is required to grade the severity or toxicity of each AE.

Investigators will reference the National Cancer Institute Common Terminology Criteria for AEs (NCI-CTCAE) (Version 4.03), a descriptive terminology that can be used for AE reporting.

A general grading (severity/intensity; hereafter referred to as severity) scale is provided at the beginning of the above referenced document, and specific event grades are also provided.

If the severity of an AE is not specifically graded by NCI-CTCAE, the Investigator is to use the general NCI-CTCAE definitions of Grade 1 through Grade 5 following his or her best medical judgment.

The 5 general grades are:

- Grade 1 or Mild
- Grade 2 or Moderate
- Grade 3 or Severe
- Grade 4 or Life-threatening

Document No. CC	C O N F I D E N T I A L I N F O R M A T I O N	24/54	
	Global Version ID: CCI		

• Grade 5 or Death

According to Sponsor convention, any clinical AE with severity of Grade 4 or 5 must also be reported as an SAE. However, a laboratory abnormality of Grade 4, such as anemia or neutropenia, is considered serious only if the condition meets one of the seriousness criteria described below.

If death occurs, the primary cause of death or event leading to death should be recorded and reported as an SAE. "Fatal" will be recorded as the outcome of this specific event and death will not be recorded as separate event. Only, if no cause of death can be reported (for e.g., sudden death, unexplained death), the death per se might then be reported as an SAE.

Investigators must also systematically assess the causal relationship of AEs to the study intervention using the following definitions. Decisive factors for the assessment of causal relationship of an AE to the study intervention include, but may not be limited to, temporal relationship between the AE and the study intervention, known side effects of the study intervention, medical history, concomitant medication, course of the underlying disease, study procedures.

- **Unrelated:** Not reasonably related to the study intervention. The AE could not medically (pharmacologically/clinically) be attributed to the study intervention under study in this clinical study protocol. A reasonable alternative explanation must be available.
- **Related:** Reasonably related to the study intervention. The AE could medically (pharmacologically/clinically) be attributed to the study intervention under study in this clinical study protocol.

Abnormal Laboratory Findings and Other Abnormal Investigational Findings

Abnormal laboratory findings and other abnormal investigational findings (e.g., on an electrocardiogram [ECG] trace) should not be reported as AEs unless they are associated with clinical signs and symptoms, lead to treatment discontinuation or are considered otherwise medically important by the Investigator. If a laboratory abnormality fulfills these criteria, the identified medical condition (for e.g., anemia or increased alanine aminotransferase) must be reported as the AE rather than the abnormal value itself.

Serious Adverse Events

An SAE is any untoward medical occurrence that at any dose:

- Results in death
- Is life-threatening. ("Life-threatening" refers to an event in which the participant is at risk of death at the time of the event, not an event that hypothetically might have caused death if it was more severe)
- Requires inpatient hospitalization or prolongs an existing hospitalization
- Results in persistent or significant disability or incapacity
- Is a congenital anomaly or birth defect

Document No. CC	C O N F I D E N T I A L I N F O R M A T I O N	25/54	
	Global Version ID: CC		

• Is otherwise considered to be medically important. (Note: Important medical events that may not result in death, be life-threatening, or require hospitalization may be considered as SAEs when, based upon appropriate medical judgment, they may jeopardize the participant or may require medical or surgical intervention to prevent one of the outcomes listed above. Examples of such events include allergic bronchospasm requiring intensive treatment in an emergency room or at home, blood dyscrasias or convulsions that do not result in inpatient hospitalization, or the development of drug dependency or drug abuse).

In this clinical study, any late spontaneous abortion, fetal death in utero, ectopic pregnancy, chronic fetal distress, stillbirth, neonatal death, or prematurity-related complication more than is typical for prematurity should be considered as an SAE (see Section 7.4.2).

For the purposes of reporting, any suspected transmission of an infectious agent via a study intervention is also considered an SAE, as described in Section 7.4.1.4.

Events that Do Not Meet the Definition of an SAE

Elective hospitalizations to administer, or to simplify study treatment or study procedures (e.g., an overnight stay to facilitate chemotherapy and related hydration therapy application) are not considered SAEs. However, all events leading to unplanned hospitalizations or unplanned prolongation of an elective hospitalization (e.g., undesirable effects of any administered treatment) must be documented and reported as SAEs.

Events Not to Be Considered as AEs/SAEs

Medical conditions present at the initial study visit that do not worsen in severity or frequency during the study are defined as Baseline Medical Conditions and are not to be considered AEs.

AE/SAEs Observed in Association with Disease Progression

Progression of the disease/disorder being studied assessed by measurement of lesions on radiographs or other methods as well as associated clinical signs or symptoms (including laboratory abnormalities) should not be reported as an (S)AE, unless the participant's general condition is more severe than expected for the participant's condition and/or unless the outcome is fatal within the adverse event reporting period (as defined in Section 7.4.1.3).

Adverse Events of Special Interest

No adverse events of special interest have been identified.

7.4.1.2 Methods of Recording and Assessing Adverse Events

At each study visit, the participant will be queried on changes in his or her condition. During the reporting period, any unfavorable changes in the participant's condition will be recorded as AEs, whether reported by the participant or observed by the Investigator. Adverse events that are ongoing during transition from the VX13-970-002 study will be recorded at enrollment to ensure the outcome and end date of the AE are captured.

Document No. CC	C O N F I D E N T I A L I N F O R M A T I O N	26/54
()	Global Version ID: CC	

Complete, accurate and consistent data on all AEs experienced for the duration of the reporting period (defined below) will be reported on an ongoing basis in the appropriate section of the eCRF. All SAEs must be additionally documented and reported using the appropriate Report Form as described in Section 7.4.1.4.

It is important that each AE report include a description of the event, its duration, onset and resolution dates (and also onset and resolution times when it is important to assess the time of AE onset relative to the recorded study intervention administration time), its severity, its causal relationship with the study intervention, any other potential causal factors, any treatment given or other action taken, including dose modification or discontinuation of the study intervention, and its outcome. In addition, serious cases should be identified and the appropriate seriousness criteria documented.

Specific guidance can be found in the eCRF Completion and Monitoring Conventions provided by the Sponsor.

7.4.1.3 Definition of the Adverse Event Reporting Period

The AE reporting period for safety surveillance begins when the participant is initially enrolled in the study (date of first signature of informed consent/date of first signature of first informed consent) and continues until 28 days after the last administration of berzosertib.

Any SAE assessed as related to berzosertib must be reported whenever it occurs, irrespective of the time elapsed since the last administration of berzosertib.

7.4.1.4 Procedure for Reporting Serious Adverse Events

Serious Adverse Events

In the event of any new SAE occurring during the reporting period, the Investigator must immediately (within a maximum of 24 HOURS after becoming aware of the event) inform the Sponsor or its designee using the electronic SAE report form in the Electronic Data Capture (EDC) system. Reporting of SAEs using a paper report form is required as a back-up method only for an EDC system failure. Names, addresses, and telephone and fax numbers will be included on the paper form. All information from the paper form must be transcribed into the electronic form as soon as the system becomes available.

In exceptional circumstances, an SAE (or follow up information) may be reported by telephone; in these cases, an electronic SAE form must be completed immediately thereafter.

Relevant pages from the eCRF may be provided in parallel (e.g., medical history, concomitant drugs). Additional documents may be provided by the Investigator, if available (e.g., laboratory results, hospital report, autopsy report).

The Investigator must respond to any request for follow up information (e.g., additional information, outcome, final evaluation, other records where needed) or to any question the Sponsor/designee may have on the AE within the same timelines as those noted above for initial

Document No. CC	C O N F I D E N T I A L I N F O R M A T I O N	27/54
	Global Version ID: CCI	

reports. This is necessary to ensure prompt assessment of the event by the Sponsor or designee and (as applicable) to allow the Sponsor to meet strict regulatory timelines associated with expedited safety reporting obligations.

Requests for follow up will usually be made via the Study Monitor, although in exceptional circumstances the drug safety department may contact the Investigator directly to obtain further information or to discuss the event.

7.4.1.5 Safety Reporting to Health Authorities, Independent Ethics Committees/Institutional Review Boards and Investigators

The Sponsor will send appropriate safety notifications to Health Authorities in accordance with applicable laws and regulations.

The Investigator must comply with any applicable site-specific requirements related to the reporting of SAEs (particularly deaths) involving study participants to the IEC/IRB that approved the study.

In accordance with ICH GCP, the Sponsor/designee will inform the Investigator of "findings that could adversely affect the safety of participants, impact the conduct of the study or alter the IEC's/IRB's approval/favorable opinion to continue the study." In particular and in line with respective regulations, the Sponsor/designee will inform the Investigator of AEs that are both serious and unexpected and are considered to be related to the administered product (suspected unexpected serious adverse reactions). The Investigator should place copies of Safety Reports in the Investigator Site File. National regulations with regard to Safety Report notifications to Investigators will be taken into account.

When specifically required by regulations and guidelines, the Sponsor/designee will provide appropriate Safety Reports directly to the concerned lead IEC/IRB and will maintain records of these notifications. When direct reporting is not clearly defined by national or site-specific regulations, the Investigator will be responsible for promptly notifying the concerned IEC/IRB of any Safety Reports provided by the Sponsor/designee and of filing copies of all related correspondence in the Investigator Site File.

For studies covered by the European Directive 2001/20/EC, the Sponsor's responsibilities regarding the reporting of SAEs/ Suspected unexpected serious adverse reaction/ Safety Issues will be carried out in accordance with that Directive and with the related Detailed Guidance documents.

7.4.1.6 Monitoring of Participants with Adverse Events

Adverse events are recorded and assessed continuously throughout the study (see Section 7.4.1.3) and are assessed for final outcome at Safety Follow Up visit to be scheduled 28 (+7) days after the last administration of berzosertib. All SAEs ongoing at the Safety Follow Up visit must be monitored and followed up by the Investigator until stabilization or until the outcome is known, unless the participant is documented as "lost to follow up". Reasonable attempts to obtain this

Document No. CC	C O N F I D E N T I A L I N F O R M A T I O N	28/54	
	Global Version ID: CCI		

information must be made and documented. It is also the responsibility of the Investigator to ensure that any necessary additional therapeutic measures and follow up procedures are performed.

7.4.2 Pregnancy and In Utero Drug Exposure

Only pregnancies considered by the Investigator to be related to the study intervention (e.g., resulting from a drug interaction with a contraceptive medication) are considered to be AEs. However, all pregnancies with an estimated conception date during the period defined in Section 7.4.1.3 must be recorded by convention in the AE page/section of the eCRF. The same rule applies to pregnancies in female participants and to pregnancies in female partners of male participants. The Investigator must notify the Sponsor/designee in an expedited manner of any pregnancy using the Pregnancy Report Form, which must be transmitted according to the same process as described for SAE reporting in Section 7.4.1.4.

Investigators must actively follow up, document and report on the outcome of all these pregnancies, even if the participants are withdrawn from the study.

The Investigator must notify the Sponsor/designee of these outcomes using the Pregnancy Report Form. If an abnormal outcome occurs, the SAE Report Form will be used if the participant sustains an event and the Parent-Child/Fetus Adverse Event Report Form if the child/fetus sustains an event.

Any abnormal outcome must be reported in an expedited manner as described in Section 7.4.1.4, while normal outcomes must be reported within 45 days after delivery.

In the event of a pregnancy in a participant occurring during the course of the study, the participant must be discontinued from study medication immediately. The Sponsor/designee must be notified without delay and the participant must be followed as mentioned above.

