5.7 Definition of End of Study

This rollover study will be ongoing while any participant is receiving berzosertib. The end of the study will be the day when the last participant has completed the Safety Follow Up visit to be scheduled 28 (+7) days after the last administration of berzosertib.

The Sponsor may terminate the study at any time once access to berzosertib for participants still benefiting is provisioned via expanded access, marketed product or another mechanism of access as appropriate.

6 Study Intervention

Study intervention is any investigational intervention(s), marketed product(s), placebo, or medical device(s) intended to be administered to a study participant per the study protocol.

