6.4.4.2 Contraception

Women of childbearing potential and males must use a highly effective method of contraception (i.e., methods with a failure rate of less than 1% per year when used consistently and correctly) as detailed below throughout the study and for 6 months after the last dose of assigned treatment.

All participants must undergo appropriate contraceptive counselling. The Investigator or any skilled representative of the study site should counsel participants on the most effective method(s) for avoiding pregnancy during the study.

Men

Acceptable contraceptive methods must be used from Screening visit through 6 months after last dose of the study intervention, and include the following:

- True abstinence (abstinence of any sexual intercourse, when in line with the preferred and usual lifestyle of the participant). Periodic abstinence (e.g., calendar, symptothermal, postovulation methods) and withdrawal are not acceptable methods of contraception.
- Condom with or without spermicide. In addition, the female partner must use a highly effective contraception method as outlined in Appendix I.
- Surgical sterilisation (vasectomy) with a negative sperm post-vasectomy semen analysis; If the absence of sperm has not been confirmed, men must use a condom and their female partner must use a highly effective contraception method as outlined in Appendix I.

Men must not donate sperm from Screening visit through 6 months after last dose of the study intervention.

Document No. CC	C O N F I D E N T I A L I N F O R M A T I O N	19/54	
	Global Version ID: CCI		

Women of Nonchildbearing Potential

Women in the following categories are not considered women of childbearing potential:

- 1. Premenopausal female with 1 of the following:
 - Documented hysterectomy
 - Documented bilateral salpingectomy
 - Documented bilateral oophorectomy

Note: Documentation can come from the site personnel's: review of participant's medical records, medical examination, or medical history interview.

- 2. Premenarchal
- 3. Postmenopausal female
 - Females who are postmenopausal (age-related amenorrhea ≥ 12 consecutive months and increased follicle-stimulating hormone (FSH) > 40 mIU/mL), or who have undergone hysterectomy or bilateral oophorectomy are exempt from pregnancy testing. If necessary to confirm postmenopausal status, a follicle-stimulating hormone will be drawn at Screening.

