 - Females on hormone replacement therapy (HRT) and whose menopausal status is in doubt will be required to use one of the non-hormonal highly effective contraception methods if they wish to continue their hormone replacement therapy during the study. Otherwise, they must discontinue hormone replacement therapy to allow confirmation of postmenopausal status before study enrollment.

All other female participants (including participants with tubal ligations and participants who do not have a documented hysterectomy) will be considered to be of childbearing potential.

Women of Childbearing Potential

A highly effective contraception as outlined in Appendix I must be used before start of first dose of study treatment, during the treatment period and for at least 6 months after the last dose of study treatment.

The following contraception methods are not considered to be highly effective birth control methods and must not be used:

- Progestogen-only oral hormonal contraception, where inhibition of ovulation is not the primary mode of action
- Male or female condom with or without spermicide
- Cap, diaphragm or sponge with spermicide
- Combination of male condom with either cap, diaphragm or sponge with spermicide (double barrier methods).

Document No. CC	C O N F I D E N T I A L I N F O R M A T I O N	20/54
	Global Version ID: CCI	

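### Does the 28-day pregnancy recording window leave conceptions later in the 6-month contraception period unreported?

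*Protocol*

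**What the plan says.** Protocol Section 7.4.2 sets several duties for pregnancies, in participants and in partners of male participants.

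- **Recording.** "all pregnancies with an estimated conception date during the period defined in Section 7.4.1.3 must be recorded by convention in the AE page/section". Section 7.4.1.3 starts that period at informed consent, and it "continues until 28 days after the last administration of berzosertib".
- **Notification.** "The Investigator must notify the Sponsor/designee in an expedited manner of any pregnancy using the Pregnancy Report Form". No conception window is attached.
- **Outcome follow-up.** "Investigators must actively follow up, document and report on the outcome of all these pregnancies", also after a participant's withdrawal. Abnormal outcomes are expedited, and normal ones are due within 45 days of delivery.

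Section 6.4.4.2 requires contraception in women of childbearing potential and in men "throughout the study and for 6 months after the last dose of assigned treatment". It repeats the requirement for women: "during the treatment period and for at least 6 months after the last dose of study treatment".

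Two other provisions bear on the point. Section 7.4.1.3 adds that "Any SAE assessed as related to berzosertib must be reported whenever it occurs, irrespective of the time elapsed since the last administration of berzosertib". Section 5.7 fixes the close of the study: "The end of the study will be the day when the last participant has completed the Safety Follow Up visit", which is scheduled 28 (+7) days after the last dose.

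The SAP does not mention pregnancy. Its Sections 7 and 15.1 call for listings only, including a listing of all AEs.

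**The concern.** The protocol gives two post-dose periods that differ widely. By requiring contraception for 6 months it treats conception in that time as something to prevent, yet the only conception window it names for reporting ends at day 28. No study contact is scheduled after the Safety Follow Up visit, and the last participant's visit ends the study.

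If all the duties in Section 7.4.2 were limited to the 28-day window, a conception in the third month after the last dose would need no notification and no follow-up to outcome. The rule on related SAEs would help only if the outcome were serious, judged related to berzosertib and known to the Investigator. A normal outcome, or the exposure itself, would be lost. Safety is the study's only objective, so information on in utero exposure would be a real loss.

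**Working it through.** The plan states no figure for this point. The check has a short piece of calendar arithmetic and a comparison of the text.

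**Length of the mismatch**

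Inputs: the recording window ends at day 28 (7.4.1.3), the latest Safety Follow Up visit is at 28 + 7 = day 35 (5.7), and contraception runs for 6 months (6.4.4.2). The documents do not convert months to days. I assume calendar months, so 6 months is 181 to 184 days.

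- Days of required contraception after the recording window: 181 − 28 = 153, up to 184 − 28 = 156.
- As a share of the 6 months: 153/181 = 84.5%, up to 156/184 = 84.8%.
- Days after the latest possible follow-up visit: 181 − 35 = 146, up to 184 − 35 = 149.

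These figures describe the calendar. They measure no risk, because they do not say how likely a conception is or whether it would go unreported.

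**Which duty carries the 28-day limit**

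| Duty in 7.4.2 | Pregnancies covered | Date limit in the sentence |
|---|---|---|
| Entry on the AE page | conceptions in the 7.4.1.3 period | yes, day 28 |
| Expedited notification | any pregnancy | none |
| Outcome follow-up | all these pregnancies | none of its own; depends on what *these* refers to |
| Expedited report of an abnormal outcome | any abnormal outcome | none of its own; follows from the row above |

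1. The limit is written into the recording sentence alone.
2. The notification sentence drops it. Read as written, a conception at day 90 that the Investigator learns of must be notified.
3. The follow-up sentence comes directly after the notification sentence, so the nearest antecedent of *these* is any pregnancy. The other reading goes back past that sentence to the recording window. It is possible but less natural.
4. Outcome follow-up already runs past the last visit for conceptions inside the window. A pregnancy conceived near the last dose delivers months after day 35, and its outcome must still be reported. The end of the study in 5.7 therefore does not end this duty.

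**Effect on the analysis**

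1. Under 7.4.2 a pregnancy counts as an AE only when the Investigator considers it related to the study intervention. Other pregnancies are placed on the AE page by convention.
2. Treatment-emergent AEs in protocol Section 8.5.2 run to the Safety Follow Up visit, and the endpoint in SAP Section 5 refers to 28 days after the last dose. A conception in the later interval lies outside the 28 days under either reading of *these*.
3. Both analysis sets depend on consent or dosing, and pregnancy plays no part in them. The choice of reading changes no set, endpoint or listing.

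**The case for a change.** The strongest case for a change is that Section 7.4.2 uses different scopes without linking them: the AE reporting period for recording, no limit for notification, and the course of the study in its closing paragraph on participants who become pregnant. A site could take the first as governing all of them. The rule on related SAEs does not fill the gap, since Section 7.4.1.4 otherwise ties the reporting of new SAEs to the reporting period. Nothing scheduled after day 35 would bring a later pregnancy to light. One sentence would settle the matter, and Sections 2 and 3.1 allow sites and participants to be added.

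Part of this stands. The antecedent of *these* is not explicit, and no study contact falls in the last 146 to 149 days of the contraception period.

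The rest is weaker. Notification is not unclear on its face. A recording window and a contraception period serve different purposes, and nothing in the protocol says they must coincide. Variation between sites has little room where a single UK site was expected, and any addition needs an amendment, at which point the wording can be tidied. Section 7.1.3 describes treatment and disease monitoring under institutional standards, so clinical contact may continue without study visits. An instruction to participants to report later pregnancies may also sit in the consent pages, which were not available for this review, so its absence cannot be inferred.

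A change also carries a risk. Tying notification to the end of the contraception period would replace a duty that has no end date with one that has. Moving AE-page recording to 6 months would bring it into conflict with the end of study in 5.7.

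**Conclusion.** No change to the plan is needed. The two periods differ by 153 to 156 days, assuming calendar months, but only AE-page recording stops at day 28. Notification covers any pregnancy without a date limit, and the more natural reading of the follow-up duty covers the same pregnancies. Followed as written, the plan gives no wrong result and loses no endpoint data.

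The remaining doubt concerns one word. It matters only for a conception after day 28 that comes to the Investigator's notice, and the notification duty would already have brought that case to the sponsor, who can ask for the outcome. The amendment history reports one enrolled participant at Amendment 2, whose sex and childbearing potential the documents do not give, so the practical effect may be nil.

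If the protocol is amended for another reason, it could usefully say that outcome follow-up applies to every pregnancy notified under 7.4.2, with the notification duty not narrowed and AE-page recording left as it is. That is optional. This conclusion takes no position on how long contraception should last.
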